6.1 Study Agent Description

6.1.1 Acquisition

The complete Melody® assay collection kit consists of 25 single-use tear collection pouches and return shipping materials. The complete Melody® collection kit used at study sites will be obtained from Namida Lab, Inc. The collection kit components for tear sample collection and return shipping will be acquired directly from their production facilities by Namida Lab, Inc. According to participant enrollment rates, kits will be disbursed to the site investigator. Disbursement schedules will be arranged between Namida Lab, Inc. and study sites. (Appendix F)

6.1.2 Formulation, Appearance, Packaging, and Labeling

The component products included for single-use tear collection are Schirmer strips, collection tubes, and sterile 1x PBS solution. Components for tear sample collection will be in a sealed, tamper-proof pouch with only one set of single-use materials. The pouches will not use a commercial appearance. A label will be affixed to each complete Melody® collection kit box and single-use pouch with large text stating that the products are for the VIOLA Clinical Utility Study Only.

The complete Melody® collection kit box will include, if applicable: the name of the product(s), a model number(s), a description of the product(s), safety, use, storage information, and manufacturer contact information. In addition, if applicable, any standard product manual package inserts will be included. The inserts detail safety information, a description of the product, directions for use, technical support, product specifications, regulatory statements, a component list, and packaging symbol and definition legends.

An affixed label will instruct users to consult an additional study-specific package insert that will also be included for use modifications on this insert. (Appendix F) This package insert will contain the name and description of this clinical study, new directions for use detailing the study indications and study procedure, and contact information for the sponsor-investigator and site investigators.

6.1.3 Product Storage and Stability

No seal will be broken until the site clinician is ready to collect the tear sample from the participant. Expiration dates will be verified before any seal is broken. According to the instruction manual specifications for temperature, humidity, and pressure, collection kits will be housed in a secure, designated location at the study sites. The collection kits will only be accessible to trained study personnel at the site until use.

6.1.4 Administration of Study Agent

All site investigators, clinicians, and personnel will receive hands-on training for the appropriate tear collection method and the proper time frame for the return shipment of tear samples. The Instructions for Use (IFU) will be available at all study sites and included in the collection kit box. (Appendix E)

6.1.5 Results of Study Agent Administration

In addition to the tear sample collection, sites will receive the participant Melody® result reports. The participant Melody® assay results will be returned digitally through a secure and encrypted messaging platform. Each site will have a designated inbox and will only have access to its site-specific participants. (Appendix I)

6.2 Study Agent Accountability Procedures

According to the disbursement schedule, collection kits and return shipping materials will be distributed to the study sites, which will specify ownership, storage, and use. The kit materials will be received by site personnel who have been trained in the safe handling and proper interim storage requirements. According to the study protocol and any site policies, the study site

personnel will maintain the proper receipt and transfer of all study products.

Should study products be unused and not defective or expired, they will be assigned to the next applicable study participant should the product not expire before the anticipated next enrollment. Defective, damaged, or expired products will be reported to Namida Lab, Inc. and disposed of or otherwise processed according to site-specific and manufacturer policies.

7. Study Procedures and Schedule

7.1 Study Procedures / Evaluations

7.1.1 Study Specific Procedures

All procedures listed are specific to the study and not considered part of standard clinical care. Specific questions and content are provided in the protocol appendix.

- Participant's informed consent will be obtained electronically through Namida Lab, Inc. mobile app if the participant has access to a device.*
- Study participant background questionnaire (Demographics, Medical History, Medication History, Family Medical History)
- Biological specimen collection and laboratory evaluation. (Melody® assay: tear sample collection)
- A discussion/medical consultation of the Melody® assay results will be provided to the participant.
- Administration of questionnaires regarding the assessment of study agent, Melody®, and patient-reported outcomes.

*The study sites will have devices on-site or permit paper submissions for participants who do not have their own devices.

7.1.2 Mobile App Eligibility and Enrollment Procedures

The potential participant will first download the Namida Lab, Inc. app. The app will automatically ensure compatibility with the iPhone iOS version and Android version. If compatible, the participant will continue forward in the app. (Appendix R). **See 7.1.6 for alternatives to digital.**

The participant will advance to a screen for new user enrollment to create a secure user account within the Namida Lab, Inc. mobile app. The participant will select the VIOLA Study from the list of available studies. The app will require a digital authentication token to determine eligibility for the study, which participants will receive from Namida Lab, Inc. during recruitment.

The study anticipates a substantial volume of participants screened and consented in the initial days following study opening. There is a potential risk of overwhelming the study infrastructure if all participants can instantly enter the study. To maintain operational efficiency, the study monitors will use an enrollment metering schema.

Participants eligible for inclusion may be delayed in consent and enrollment (participant recruitment and enrollment portion of the study). Enrollment metering will be adaptable based on study and clinical bandwidths, with metering instituted by invitation to consent.

7.1.3 Mobile App Consent, Baseline Demographics, and Medical History Collection

The Namida Lab, Inc. mobile application allows for secure and remote electronic consent and

participation in clinical research and utility studies. The Namida Lab, Inc. app utilizes the ResearchKit and ResearchStack open-source frameworks on the iOS and Android platforms.

As in other mobile-mediated research and studies, the informed consent process in the Namida Lab, Inc. app is conducted remotely in an entirely self-administered setting with no required contact with the study personnel before consent and enrollment. The approach to informed consent for the study has been adapted accordingly to ensure the ethical requirement of informedness, i.e., that participants are adequately informed about the study before participation, is met. **See 7.1.6 for alternatives to digital.**

Potential candidates and enrolled participants will be able to contact study site personnel and have the ability to ask questions and request clarifications at any time before or during the study. This site personnel will be available from the study start date until study closure. Participants who successfully pass the eligibility criteria will be directed to a page requesting their consent to participate. Participants will be asked to read and sign the informed consent and authorization document within the app if they agree to volunteer or participate. A copy of the signed informed consent and authorization document will be available for review and download to the participant via the app.

The participant will be considered 'enrolled' from this point. After consenting to participate, the participant will be directed to complete a brief questionnaire to collect self-reported baseline demographics and medical history. (Appendix D)

7.1.4 Overall Procedures for Enrolled Participants

After completing the baseline demographics and medical history questionnaires, the participant will schedule a sample collection appointment/walk-in at their study site. The study personnel will collect the tear sample and return it to Namida Lab, Inc. Namida Lab, Inc. will perform the Melody® assay lab-developed test and return the participant's results to their study site. The site clinician will review the Melody® results with the participant.

The participant will receive a notification informing them that the exit questionnaire has been published and is available to complete. Upon completing the exit survey, the participant will be notified that their participation in the study is complete. They will receive instructions to claim the \$25 Walmart gift card.

7.1.5 Standard of Care Study Procedures

The Standard of Care is determined by the site investigator, clinicians, and personnel. It is not within the scope of our expertise or study endpoints to define the participant's path of care beyond the safe collection of the tear sample and medically supervised consultation of Melody® results.

7.1.6 Alternatives to Study Participation without Mobile Application

If the participant does not have access to a smartphone/tablet and/or affordable cellular data plans, they will not be excluded from the study. All sites will have a Namida Lab, Inc. provided tablet that participants may access to participate in the study.

If the participant chooses not to use the designed digital path, Namida Lab, Inc. will provide the

necessary physical copies of the study material. Each site will have physical copies of all study material, i.e., informed consent and questionnaires. The study personnel will engage with participants in the study using a traditional clinical trial model.

7.2 Laboratory Procedures / Evaluations

7.2.1 Clinical Laboratory Evaluations

Melody®, a tear-based screening assay for breast cancer developed and validated by Namida Lab, Inc., a high complexity CLIA certified lab.

7.2.2 Specimen Preparation, Handling, and Storage

The trained clinician and personnel will follow the step-by-step tear sample collection Instructions for Use (IFU) at the study site. (Appendix E)

At Namida Lab, Inc., the trained laboratory personnel will follow the step-by-step Standard Operating Procedure (SOP) for specimen preparation, handling, and storage. (Appendix G)

7.2.3 Specimen Shipment

After the tear sample has been collected from the participant, it should be placed in the pre-paid FedEx envelope for overnight shipment to Namida Lab, Inc. The sample must be mailed to Namida Lab, Inc. at [name] (Attn: [name]) on the same day it was collected.

Namida Lab, Inc. will accept samples Monday through Thursday, excluding holidays. There are no special shipping requirements such as cold storage or biospecimen labels. The postage is pre-paid, and Namida Lab, Inc. provides all shipping materials.

7.3 Study Schedule

7.3.1 Recruitment / Enrollment

Participant Recruitment / Enrollment (Study Intervention)

- Obtain informed consent of the potential participant.
- Obtain medical history to determine eligibility based on inclusion/exclusion criteria.
- Schedule visits for participants who are eligible and available for the duration of the study.
- Provide participants with site-specific instructions needed to prepare for the first study visit.

7.3.2 Baseline Assessments / Study Intervention

(Enrollment) / Baseline Visit / Study Intervention

- Obtain informed consent of potential participants verified by signature on study informed consent form.
- Verify inclusion/exclusion criteria.
- Obtain demographic information, medical history, and medication history.
- Collect tear (lacrimal) fluid sample for Melody® assay.
- Site-specific procedures, instructions provided to participants, observations after tear collection.

7.3.3 Follow-Up / Final Study Visit

Follow-up Visit (Assessment of Study Endpoints / Safety)

- Site-specific procedures and instructions provided to participants to review assay results: Melody® Scale, Score, and Classification.

Script-reporting results

*I received your test results back, and your Melody® classification is **** (High or Low), and your score is***.*

*According to the scale provided by Namida Lab, Inc., in the range, you fall into of *** to *** ***percent of women had breast cancer and ****were normal.*

(It is up to you and your practice's discretion to make recommendations for the next steps in screening)

*This practice follows the *** guidelines, and for a woman of your age and family history, we recommend a screening mammogram.*

(If your practice typically schedules screening mammograms on behalf of patients, you may offer to do that now.)

A member of the Namida Lab, Inc. clinical team will reach out to you with the next steps for the VIOLA Study.

Final Study Visit

- Site-specific procedures and instructions are provided to participants to complete the exit questionnaire(s).
- Site-specific final instructions to the participant if additional care is required.

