2.1 Background Information

Determining the Sensitivity and Specificity of the Melody® assay

ROC curve for Breast Cancer vs. Healthy Controls.

Analysis of the development data set was outsourced to the statistical firm Elite Research, Irvine, TX, to develop an algorithm and scoring system by which samples could be classified. Stepwise linear regression analysis of the development data set (224 healthy controls and 45 confirmed breast cancer samples) was used to determine relevant covariates and produce a screening algorithm and scoring system. The coordinates of the ROC curve were used to select a diagnostic threshold of 0.1.

A smaller validation sample set (167 healthy controls and 15 breast cancer samples) was used to test the algorithm and diagnostic cutoff, followed by clinical validation of Melody® in the CLIA lab with 50 healthy control samples and 50 breast cancer samples.

False-positive and false-negative rates were determined strictly based on Melody® classification, not score. Tear samples were collected at the time of imaging procedures, tested at Namida Lab, Inc., and assigned a score and classification before confirming the final diagnosis from our clinical partner. Once received, the final diagnosis was then compared to the classification of High or Low determined through the Melody® algorithm.

Patients who were given a Low Melody® classification but tested positive for breast cancer were

considered false negatives. This occurred for 8% of samples. Patients were given a High Melody® classification, but no area of concern or suspicion was detected on their mammogram classified as false positive. This occurred in 46% of samples.

A standard screening population would typically be entering the continuum of care for a screening mammogram and would fall between the ages of 40-70. All healthy controls were collected at the time of the screening mammogram. Breast cancer samples were typically collected at the time of biopsy or diagnostic MRI. Previous imaging procedures were provided by clinical partners when providing diagnostic information.

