Tear samples are collected using a small strip of filter paper, called a Schirmer strip, a Class I Medical Device typically used to test for dry eye. The strips have been repurposed for our need to collect tear (lacrimal) fluid and the subsequent proteins from the ocular cavity following protocols outlined in the literature (3, 4).

Tear collection is conducted through the following steps (Figure 1):

1. The strip is placed in the participants' lower eyelid, and having a foreign object in the eye will cause the eye to water.
(The tear (lacrimal) fluid released washes the inner surface of the eyelid and the ocular lens itself, allowing proteins to adhere to the strip.)
2. The strip is left until the liquid reaches the 25 mm mark or 5 minutes has passed.
3. The strip is then placed in a tube containing a buffered solution and is shipped overnight to Namida Lab, Inc.

Figure 1: Collection of tear sample.

[figure not shown]
Part 2: Clinical Lab assay

During shipment, the proteins leave the strip and go into the buffered solution in the tube. It is

this solution that is evaluated using standard ELISA techniques in the high complexity CLIA lab. Namida Lab, Inc. is outfitted with a Hamilton Star Plus automated ELISA system. The data generated from the ELISA assay is used together with demographic information to generate a Melody® score. The score is then compared to the diagnostic threshold, and classification of High or Low is reported.

Site clinicians will receive a report containing both the score and the classification for the participant. In addition, the site clinicians will be given a Melody® scale (Figure 2) as a reference to use when discussing the results with the study participants. (Appendix I) It will be up to the individual site clinician's discretion to provide participants with a copy of their test results.

*Figure 2: Melody® Scale**

*The Melody® scale was generated using 705 samples evaluated during development and validation. Percentages in each range show the distribution of normal and breast cancer patients that fall within each range. The distribution of scores along the scale will continually be updated as new data is collected.

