4.1 Description of the Study Design

Analytical Observational Study

In analytical observational studies, researchers try to establish an association between

exposure(s) and outcome(s) (10). Depending on the direction of inquiry, these studies can be directed forward, known as cohort studies, or backward known as case-control studies.

The VIOLA Study is an analytical study designed to quantify a relationship or association between two variables – an exposure and an outcome. The exposure, Melody®, is pre-determined for all participants to receive as opposed to experimental studies where an investigator assigns each participant to receive or not receive a particular exposure.

The VIOLA Study was designed to be directed forward using a cohort population at multiple study sites. A cohort is defined as a "group of people with a shared characteristic." In cohort studies, different groups of people with varying levels of exposure are followed over time to evaluate the occurrence of an outcome. Melody® does not have varying levels of exposure but is an overall new exposure for the population.

This observational study will not dictate the cancer screening regimens that the site clinicians and participants utilize. Instead, this study collects data on individuals' cancer screening practices, cancer outcomes, and other factors if needed. Because no regimens are dictated, the VIOLA Study can capture information about and evaluate various cancer screening practices, including the use of different tests or cancer screening regimens.

The association of exposure to outcome this study is attempting to define: How does the use of Melody® before mammography affect participation rates in breast cancer screening?

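### The result script presents percentages from case-enriched development samples as the share of women with cancer, which misinforms average-risk participants

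*Protocol*

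**What the plan says.** Section 7.3.3 (Follow-Up / Final Study Visit) contains a script for reporting results. After the classification and score, the clinician says "According to the scale provided by Namida Lab, Inc., in the range, you fall into of", with blanks for the two ends of the score range. A blank figure follows, then "percent of women had breast cancer and", and then a figure for normal women. The next scripted statement recommends a screening mammogram.

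The note to Figure 2 in section 2.1 gives the source of those figures: "The Melody® scale was generated using 705 samples evaluated during development and validation". It describes them as follows: "Percentages in each range show the distribution of normal and breast cancer patients that fall within each range". It mentions no adjustment to a screening prevalence.

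Section 2.1 itemises three sample sets: "224 healthy controls and 45 confirmed breast cancer samples" for development, "167 healthy controls and 15 breast cancer samples" for a first validation, and "clinical validation of Melody® in the CLIA lab with 50 healthy control samples and 50 breast cancer samples". Cancer samples were typically taken at biopsy or diagnostic MRI, and controls at screening mammography. The Protocol Summary describes the VIOLA population as asymptomatic, average-risk women aged 40 to 74.

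Section 4.1 poses the study question: "How does the use of Melody® before mammography affect participation rates in breast cancer screening".

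**The concern.** In samples assembled by known disease status, the proportion with cancer is set by the sampling, not by how common cancer is among screened women. A within-range percentage from such samples is not the probability that applies to an average-risk woman whose score falls in that range. The script ties the percentage to the range she falls into and does not say that the women behind it were selected for having cancer. She will naturally hear it as information about herself.

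Two things are at stake. Participants may be given a misleading cancer figure, and on the stated specificity 46% of those without cancer will be classed High. In addition, result delivery is part of the exposure whose effect on mammography uptake is being studied. An inflated figure given just before the mammogram recommendation could itself raise uptake, and the analysis could not separate that from an effect of correctly reported results.

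**Working it through.** **The plan's own figures.** Section 2.1 gives sensitivity 92% and specificity 54%. With 50 cancers and 50 controls these match 46/50 = 92% and 27/50 = 54% (the counts are inferred, since only percentages are given). The complements, 8% and 46%, are the error rates stated in sections 2.1 and 2.3.1. Table 2 lists 52 rather than 50 samples for sensitivity, and 48/52 = 92.3% agrees as well.

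**Cancer share of the samples.**
- Healthy: 224 + 167 + 50 = 441. Cancer: 45 + 15 + 50 = 110. Share: 110/551 = 20.0% (112/553 = 20.3% with the Table 2 count).
- The scale uses 705 samples, so 705 − 551 = 154 are not itemised.
- If all 551 are among the 705, the share lies between 110/705 = 15.6% (all 154 healthy) and 264/705 = 37.4% (all 154 cancer).

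**Reading 1: shares within a range.** The percentage is P(cancer | range), with odds equal to the likelihood ratio of the range times the cancer odds of the sample. The range likelihood ratios are not given, so the High/Low classification serves as an illustration:

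P(cancer | High) = 0.92p / (0.92p + 0.46(1 − p))

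P(cancer | Low) = 0.08p / (0.08p + 0.54(1 − p))

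The protocol gives no prevalence of cancer at a single screen. The values 0.3%, 0.5% and 1% are assumptions.

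| p | Cancer given High | Cancer given Low |
|---|---|---|
| 15.6% (sample, lower bound) | 27.0% | 2.7% |
| 20.0% (itemised samples) | 33.3% | 3.6% |
| 37.4% (sample, upper bound) | 54.5% | 8.1% |
| 0.3% (assumed) | 0.6% | 0.04% |
| 0.5% (assumed) | 1.0% | 0.07% |
| 1% (assumed) | 2.0% | 0.15% |

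At the lower-bound share of 15.6%, the High figure is 14 times too large at 1% prevalence and 45 times at 0.3%. At an assumed prevalence of 2% it is still 27.0/3.9, about 7 times.

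**The multiple differs by score range.** At a 20.0% sample share:
- A range with likelihood ratio 1 shows 20.0% against 0.3% to 1%, which is 67 to 20 times too large.
- A range with likelihood ratio 10 shows 71.4% against 2.9% to 9.2%, which is 24 to 8 times too large.

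The multiple shrinks in high-score ranges because the sample percentage cannot exceed 100%.

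**Reading 2: shares of all cancers falling in a range.** The percentage is then P(range | cancer), and the script presents it as P(cancer | range). At class level the two quantities are 92% for P(High | cancer) and 0.6% to 2.0% for P(cancer | High) at the assumed prevalences. Case enrichment is not the cause here. The error is the reversed conditional, and its size by range cannot be worked out from the protocol.

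**The case against.** The strongest objection is that Figure 2 is not shown. The script reads out a score-range percentage, whereas the 27% and 33% above belong to the High class, so nobody is scripted to say them. This stands, and those figures are an illustration only. The 154 unitemised samples and the assumed prevalence also stand as limits. Neither removes the problem. Even if the 50 clinical-validation cancers were the same women as 50 of the earlier 60, and every other sample were healthy, the share would be 60/705 = 8.5%. The High figure would then be about 16%, or 8 to 26 times too large.

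A second objection is that the script speaks in the past tense of women on the sponsor's scale and never states a personal risk. That is literally true. But the script places the listener in the range and gives no caveat about who the women were.

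Third, limits are stated elsewhere. Section 2.3.1 gives the 46% and 8% error rates, and the sample report in Appendix I says a score above 0.1 does not guarantee cancer. Neither corrects a stated cancer percentage, and section 2.1 leaves it to the clinician whether she receives a copy of her results. The consent form is not in the text at hand, so what it says about the scale cannot be checked.

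Fourth, 84% of the cancer samples came from women who entered care at screening. That bears on the type of cancer sampled, not on the proportion of cancers. Finally, section 2.1 says the scale will be updated. Adding 205 cancer-free women would give 110/910 = 12.1%, which is still enriched.

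**Conclusion.** The point holds. Under either reading of the scale, a clinician who follows the script gives an average-risk woman a percentage that is not the share of women like her who have cancer. Under the reading the script itself uses, the figure is too high. At every allocation of the 154 unitemised samples and every assumed prevalence from 0.3% to 2%, the illustrative High figure is overstated by a factor of at least about 7. This rests on the assumed prevalence, on all itemised samples being in the 705, and on 92% and 54% carrying over to screened women.

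Two stronger conclusions might be inferred, and the documents do not support them:
- **That women are told a probability 17 to 56 times too high.** Those ratios (33.3/2.0 and 33.3/0.6, before rounding) compare High-class figures at a 20% share. The percentages actually read out are unknown, the multiple varies by range, and under reading 2 it does not apply.
- **That the script is the exposure, so that correcting it would make any rise in uptake attributable to the test.** Section 4.1 names Melody as the exposure, and result delivery is only part of it. Section 10.1 compares uptake with 2019 Arkansas rates without a concurrent group, and that limit remains whatever the script says. The inflated figure is an additional source of bias.

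**What to change.** In section 7.3.3 and on the Melody scale, stop presenting the raw sample percentages as the share of women with cancer. Two ways are open:

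1. Recompute each range's percentage at a stated screening prevalence (likelihood ratio of the range times the prevalence odds, converted to a probability), and label it with that prevalence.
2. Report the score and classification with the 92% sensitivity and 54% specificity, and state that the scale comes from samples with far more cancers than a screening population.

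In either case the Figure 2 note should say whether its percentages are shares within a range or shares of all cancers and all normals, and should give the cancer and normal counts among the 705 samples.

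The cost is one reworded script passage, a reprinted scale and an IRB submission. The percentages under option 1 will be less striking. No new data are needed and no screening recommendation changes. The change should be made before results are delivered, because the analysis cannot undo what participants were told.
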